12.3 Replacement of Participants

Participants who withdraw from the study treatment will not be replaced.

Participants who withdraw from the study will not be replaced.

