5.2 Endpoints

For convenience, we give names to the following times and time windows:

- Baseline or Day 1: Date of the first study drug administration
- Study Hospitalization: Day 1 through either Day 14 or hospital discharge, whichever is first
- Observation Period: The 28-day period following first study drug administration
- Study Duration: The period from baseline until 30 days after last study drug administration

If an endpoint is to be evaluated at all three of the above time points, we use the phrase ‘at any time point’.

Endpoints are presented in a numbered list to facilitate references to endpoints when conducting the final analysis.

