7.2 Win Ratio Calculations

The standard of care treatment for COVID-19 changed with the introduction of anti-inflammatory steroids, which appear to influence D-dimer concentrations. It was therefore determined to elevate the secondary endpoint to become a co-primary endpoint. This endpoint is a composite of clinical outcomes including death, survival time, mechanical ventilation days, decrease in SpO₂/FiO₂ ratio, and cumulative COVID-19 ordinal scores.

This endpoint will be assessed nonparametrically by comparing outcomes across all possible pairs of treatment-placebo patients and evaluating a 'win ratio' using the Mann-Whitney U-statistic (Pocock et al., 2012). See Section 8.6.2.2 for details. The win proportion is interpreted as the probability that a study drug patient experiences a better outcome than a placebo patient, and in this sense, it represents the effect size for the analysis. We powered our analysis on a presumed 0.67 win proportion (i.e. a patient on study drug is twice as likely to have a better outcome as a patient on placebo). We calculated sample size requirements using the formulas provided in Yosef et al. (2019).

Because we set a 0.006 Type I error significance (alpha) for the interim analysis for benefit of D-dimer, we could only use 0.044 of the original 0.05 for the primary endpoints. We divided the 0.044 between the two co-primary endpoints, leaving a 0.022 two-sided Type I error. Accounting for a 10% dropout, we require 127 patients to have 80% power to significantly detect a win ratio of 0.67.

8 General Analysis Considerations

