9.2 Derived variables

9.2.1 Hierarchical Composite Endpoint Used in Win Ratio Analysis

The win ratio analysis of the hierarchical composite outcome requires a direct comparison of outcomes between each dipyridamole patient and placebo patient. The patient with the superior outcome is adjudicated the ‘winner’ and receives a +1 score, while the ‘loser’ scores -1. The criteria for comparison are below and are summarized in Table 3:

1. If one participant dies and one lives, the participant who does not die wins (Scenario 1)
2. If both participants die, then the participant who lives longer wins (Scenario 2)

3. If both participants die and live the same number of days, then there is a tie (Scenario 3).
4. If neither participant dies, then the participant with fewer days on ventilator wins (Scenario 4).
5. If the participants are tied after step 4, and only one of the participants has a decrease in daily average SpO₂/FiO₂ of 50 or greater, then the participant who does not have the decrease in SpO₂/FiO₂ wins (Scenario 5).
6. If the participants are tied after step 5, then the participant with lower cumulative COVID ordinal score wins (Scenario 6),
7. If the participants are tied after step 6, then their final result is a tie (Scenario 7).

Table 3. Description of Hierarchical Composite Endpoint Win Scenarios

Scenario	Death [1]	Survival [1]	Number of days on mechanical ventilation [2]	Decrease from baseline in SpO ₂ /FiO ₂ \geq 50 [3]	Sum of COVID ordinal scores [4]	Score
1	Dead					-1
	Alive					+1
2	Dead	Shorter				-1
	Dead	Longer				+1
3	Dead	Tied				0
	Dead	Tied				0
4	Alive	N/A	Longer			-1
	Alive	N/A	Shorter or None			+1
5	Alive	N/A	Tied	Yes		-1
	Alive	N/A	Tied	No		+1
6	Alive	N/A	Tied	Tied	Higher	-1
	Alive	N/A	Tied	Tied	Lower	+1
7	Alive	N/A	Tied	Tied	Tied	0
	Alive	N/A	Tied	Tied	Tied	0

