
[1] Death and survival are assessed from the time of study medication to 30 days after the last dose of study drug (a maximum of 44 days from consent). Participants are censored at the time of drop-out or the data cutoff date (if no event has occurred).
 
[2] Number of days on mechanical ventilation are counted from the time of study medication until hospital discharge. If a participant is re-hospitalized and receives ventilation, these data are not counted.
 
[3] Oxygenation measurements are collected from EHR records. Baseline is defined as the average of measurements taken between 8 hours prior to start of study medication and the start of study medication administration. A 50-point drop is defined as a participant who experiences two consecutive measures of at least 50 points below baseline. Post-baseline measurements are assessed up to and including day 44 (from consent).
 
[4] COVID ordinal scores are defined in Table 2.
						

The cumulative sum of COVID ordinal scores used in Step 6 is calculated as the time-weighted sum of daily ordinal scores, with units of ordinal score days. For example, if a subject started medication at 9:00 pm on Day 1 with a score of 4, and that score decreased to 3 at 6:00 am the next day, and that patient was discharged at noon on the third day, then the cumulative sum of ordinal scores would be:

$$\frac{\{3 \text{ hrs} \times 4 + (6 \text{ hrs} \times 4 + 18 \text{ hrs} \times 3) + 12 \text{ hrs} \times 3\}}{24 \text{ hrs/day}} = \frac{12 + (24 + 54) + 36}{24} = 5.25$$

The use of the cumulative ordinal score in Step 6 of the above algorithm is meant as a combined measure of the severity and duration of a patient's illness, since longer hospitalizations and larger daily ordinal scores will both increase the cumulative total.

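### The composite's win rules never use the censoring time, so a patient who leaves the study before discharge tends to score as a win

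*SAP*

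**What the plan says.** SAP 9.2.1 compares every dipyridamole patient with every placebo patient. The top step is "If one participant dies and one lives, the participant who does not die wins (Scenario 1"). Two deaths are ordered by survival time. Otherwise "If neither participant dies, then the participant with fewer days on ventilator wins (Scenario 4"), followed by a yes/no oxygenation drop and then the lower cumulative ordinal score. Table 3 has only dead and alive rows, and the survival column does not apply in the alive rows.

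The footnotes set the counting windows. On death: "Participants are censored at the time of drop-out or the data cutoff date (if no event has occurred"). On ventilation: "Number of days on mechanical ventilation are counted from the time of study medication until hospital discharge". The ordinal total is time-weighted and is meant to reflect duration, "since longer hospitalizations and larger daily ordinal scores will both increase the cumulative total". SAP 5.2 defines study hospitalization, over which the ordinal sum is taken, as "Day 1 through either Day 14 or hospital discharge, whichever is first".

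SAP 8.2.1 keeps every dosed patient in the analysis. SAP 8.4 deals with missing data for the mixed models and for time-to-event responses, but not for the win algorithm. SAP 7.2 sizes the endpoint as follows: "Accounting for a 10% dropout, we require 127 patients to have 80% power". Protocol 12.3 adds: "Participants who withdraw from the study will not be replaced".

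**The concern.** The footnote announces censoring, but nothing in the algorithm acts on it. No step limits a pair to shared follow-up, and no row covers a participant whose follow-up stopped early. Read literally, a patient who withdraws on Day 3 is alive and beats a patient who dies on Day 20, although nobody knows which of them lived longer. The lower tiers lean the same way, because each is a count or an ever/never event that stopping observation can only hold or reduce.

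This is a co-primary endpoint. If in-hospital drop-out differs between arms, the win proportion shifts toward the arm that loses more patients. If drop-out is equal, a true effect is diluted.

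**Working it through.** **1. Effect on each tier**

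| Tier | Leaving before discharge | Loss after discharge |
|---|---|---|
| Death | Unrecorded death; scored alive | A later death can be missed |
| Ventilator days | Count cut short | Complete by definition |
| Oxygenation drop | Less time to show one | Only a later drop can be missed |
| Ordinal sum | Sum cut short | Complete by definition |

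An illustrative simulation of the Table 3 hierarchy agrees. It assumed about 10% deaths, 10% ventilated, mean stay about 6 days, and drop-out at a random point in the stay. In-hospital drop-outs ranked on average at the 74th percentile, against the 50th with full data; about 22% still ranked below the median. Patients lost after discharge ranked at the 51st, against the 50th.

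**2. The plan's own sample size**

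Inputs from SAP 7.2: win proportion p = 0.67, two-sided alpha 0.022, power 0.80, drop-out 10%. The Noether formula for a 1:1 Mann-Whitney test gives

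N = (z₀.₉₈₉ + z₀.₈₀)² / [3(p − 0.5)²] = (2.290 + 0.842)² / (3 × 0.17²) = 113.1, so 114. Then 114 / 0.9 = 126.7, so 127.

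The stated figure reproduces. It treats drop-outs as contributing nothing, whereas the mITT analysis keeps and scores them.

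**3. No drug effect, unequal drop-out**

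Let q be the chance that a drop-out beats a completer, and dT and dP the drop-out proportions on dipyridamole and placebo. With no effect, the win proportion is 0.5 + (dT − dP)(q − 0.5). The two-sided rejection rate is Φ(z − 2.290) + Φ(−z − 2.290), with z = √(3N) × (win proportion − 0.5). Take N = 100, where enrolment stopped, and assume 15% against 5%:

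- Random time in the stay, q about 0.74: 0.5 + 0.10 × 0.24 = 0.524; z = 0.416; rejection 0.034. Direct simulation gave 0.525 and 0.034.
- Withdrawal on Days 1–4, q about 0.87: 0.537; z = 0.641; rejection 0.051. This q comes from a second simulation, assuming 12% deaths, 12% of survivors ventilated, 30% with an oxygenation drop and median stay 5.5 days.
- Upper bound, q = 1: 0.55; z = 0.866; rejection 0.078.

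The formula depends only on the difference dT − dP, so 10% against 0% gives the same results.

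**4. Equal drop-out**

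With no effect the win proportion stays at 0.5 and the error rate at 0.022. With a true 0.67 and 10% in each arm, if drop-outs carry no treatment information, q cancels:

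0.9 × 0.9 × 0.67 + 0.1 × 0.9 × [q + (1 − q)] + 0.5 × 0.1 × 0.1 = 0.5427 + 0.09 + 0.005 = 0.638.

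Power is Φ(√(3N) × (p − 0.5) − 2.290):

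- No drop-out, N = 100: Φ(17.32 × 0.17 − 2.290) = 0.74.
- 10% in each arm, all in hospital, N = 100: Φ(17.32 × 0.138 − 2.290) = 0.54.
- Drop-outs removed, N = 90: Φ(16.43 × 0.17 − 2.290) = 0.69.
- Half the drop-outs leave after discharge (assumed), so 5% in hospital per arm: win proportion 0.653, power 0.64.

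**The case against.** A reader might infer that the SAP scores drop-outs as alive. It does not say so: the word is censored, and the alive score follows from a missing rule. Protocol 15.3 cites a paper on global rank tests whose title mentions possibly censored outcomes, and the authors may have meant to compare over shared follow-up. That is possible, but the steps do not state it. Applied to death alone, it would leave ventilator days and the ordinal sum uncorrected.

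A reader might also infer that drug intolerance creates the drop-outs. The Protocol does not support that. Section 12.1 separates stopping study drug from leaving the study and keeps following patients withdrawn from treatment for an adverse event. Section 10.16 includes a record review for endpoints at early withdrawal and a call 30 days after the last dose. Oxygenation comes from the health record, and SAP 8.1 delays the final analysis until 30-day follow-up is complete for all randomized patients. These provisions narrow the affected group, though they do not guarantee data after consent is withdrawn.

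Nor does every drop-out gain. SAP 8.4 reports that a large majority of patients are discharged early. That is not drop-out, and a short ordinal sum is then the intended good result. A patient already ventilated or with a recorded oxygenation drop before leaving can still lose. The 10% in SAP 7.2 is a planning allowance with no stated timing or arm.

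All of this stands. It limits the size of the problem but does not supply the missing rule.

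**Conclusion.** The gap is real and should be closed. It concerns participants who leave before discharge with no recorded death. A claim that the composite is biased would go too far, because a shift toward one arm needs unequal or outcome-related drop-out and the documents report neither. The error rates of 0.034 to 0.051, against 0.022, rest on an assumed 15% against 5% split, all in hospital, and on simulated values of q. The power figure of 0.54 at N = 100 assumes that the whole 10% in each arm leaves before discharge; any share leaving later makes the loss smaller.

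**What to change.** In SAP 9.2.1 and Table 3, before the final analysis by arm:

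- Where either member of a pair withdrew or was lost before completing the planned window for a tier, compare that tier only over the time both were observed. Score the pair 0 if no tier decides it.
- Leave the planned windows unchanged for participants fully followed by chart and call, including those discharged early. Cutting every pair at the earlier last-observed date would discard real events. A patient last dosed on Day 3 is followed to about Day 33 and one last dosed on Day 14 to about Day 44, so a Day 40 death would be ignored in that pair.
- Add one sensitivity analysis that ranks in-hospital drop-outs with the worst survivors.

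The rule relies on each tier's window, so the ventilator-day window should be stated once. Footnote 2 of Table 3 runs it to discharge, while SAP 5.2.1 uses study hospitalization, which stops at Day 14.

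The cost is a few lines of text, slightly more programming and a few more ties. The change removes the reward for leaving but does not fully restore power, because unobserved time remains uninformative.

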5.2.1 Primary Endpoint

The first co-primary endpoint is increase in plasma D-dimer levels compared to baseline.

The second co-primary endpoint is a clinical hierarchical composite of:

- Time to death from any cause during study duration
- Number of days on mechanical ventilation during study hospitalization
- A dichotomized (yes/no) decrease in daily average SpO₂/FiO₂ ratio of at least 50 units relative to Day 1 at any time during the observation period
- Cumulative sum of COVID ordinal scores during study hospitalization

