6.4.9 Oxygen requirements

Pulse oximetry (SpO₂), oxygen requirements (mode of delivery), fraction of inspired oxygen (FiO₂), oxygen flow rate, and mode of mechanical ventilation will be recorded at least daily alongside vital signs measurement. Pulse oximetry will be measured at least twice daily.

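### The SpO2/FiO2 drop in the composite is defined in two ways in the SAP, and the footnote version makes the flag depend on how often a patient is charted

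*SAP*

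**What the plan says.** The oxygenation drop is the third level of the hierarchical co-primary endpoint, after death and ventilator days. The documents define it in more than one way.

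- **SAP 9.2.1, Table 3 footnote [3].** The readings are whatever the health record holds. The baseline is their mean over the 8 hours leading up to the first dose. The rule for a drop is: "A 50-point drop is defined as a participant who experiences two consecutive measures of at least 50 points below baseline". Follow-up for the drop runs to day 44, counted from consent.
- **SAP 9.2.1, step 5.** The pair is decided if "only one of the participants has a decrease in daily average SpO₂/FiO₂ of 50 or greater".
- **SAP 5.2.1.** A yes/no "decrease in daily average SpO₂/FiO₂ ratio of at least 50 units relative to Day 1", at any time in the observation period, which SAP 5.2 sets at 28 days from first dose.
- **Protocol 3.1.** A fall of 50 or more in the daily average compared with enrolment, through day 28 ± 1.

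Protocol 15.3 and SAP 10.3 repeat the 50-unit threshold without naming a unit of measurement.

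On reading frequency, SAP 6.4.9 says oxygen data "will be recorded at least daily alongside vital signs measurement. Pulse oximetry will be measured at least twice daily". These are minimum frequencies. No clock times, maximum or common grid are set.

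**The concern.** The footnote is the most detailed derivation a programmer has for this step, and it conflicts with the endpoint definition on unit, baseline and window.

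The conflict has consequences. If a measure is a single chart entry, two consecutive entries span about 12 hours for a patient read twice a day and about 1 hour for a patient read hourly. The closely charted patient has many more chances to meet the rule and needs only a brief dip to do so. Two patients with the same oxygenation could then be classified differently because of how closely the ward watched them. That is misclassification at a level of the hierarchy that outranks the cumulative ordinal score.

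**Working it through.** **1. Which unit does the footnote mean?** It calls the readings in the 8 hours before first dose measurements and averages them. Values averaged within 8 hours cannot be daily averages, so single chart readings is the natural meaning. Step 5 and SAP 5.2.1 say daily average, so the SAP contradicts itself.

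**2. Baseline and window.** The footnote uses an 8-hour pre-dose mean, SAP 5.2.1 uses Day 1 and protocol 3.1 uses enrolment. The footnote window ends at day 44 from consent, the SAP 5.2.1 window 28 days after first dose.

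**3. The plan's own figure (SAP 7.2).** Inputs: win proportion 0.67, two-sided alpha 0.022, 80% power, 10% dropout. The Mann-Whitney (Noether) formula gives

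N = (2.290 + 0.842)² / (12 × 0.25 × 0.17²) = 9.81 / 0.0867 = 113.1, rounded up to 114; 114 / 0.90 = 126.7, so 127.

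This reproduces N = 127. The win proportion is assumed directly, so no flag rate enters the calculation and N does not depend on the drop rule.

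**4. Dependence on charting frequency.** The documents give no reading-to-reading variability, so this step rests on assumptions. The model is a constant mean SpO2/FiO2 (no true decline) over 5 days, with normal deviations of standard deviation SD and correlation exp(−gap/6 h). Baseline is the mean of readings in the 8 hours before dose. The footnote rule flags a patient with any two consecutive readings at least 50 below baseline.

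| SD (assumed) | Rule | 12-hourly | Hourly | Difference |
|---|---|---|---|---|
| 20 | two consecutive readings | 5% | 24% | +19 points |
| 20 | time-weighted daily average | 6% | 2% | −4 points |
| 40 | two consecutive readings | 30% | 75% | +45 points |
| 40 | time-weighted daily average | 33% | 27% | −6 points |

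At SD 40 with 4-hourly readings the two rules flag 52% and 28%. Repeat runs of the footnote rule agree to about 3 points (SD 40: 27–30%, 50–52% and 75–76% at 12-, 4- and 1-hourly; SD 20 hourly: 24–27%).

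The mechanism is simple. Five days hold 10 readings at 12-hourly and 120 at hourly charting. Adjacent readings correlate exp(−12/6) = 0.14 and exp(−1/6) = 0.85 respectively, so hourly readings give both more pairs and pairs that dip together.

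A wider grid (7 days; SD 25, 40, 60; correlation time 0, 2, 6, 24 h) shows a rise from 2 to 24 readings a day in all 12 settings. The smallest is 12% to 16% (SD 25, independent readings) and the largest 31% to 85% (SD 40, 2 h). The smallest case is not monotone: 17% at 4 a day and 14% at 6 a day.

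**5. Weight of the step.** The protocol synopsis says about one-quarter of admitted patients need ventilation. If 25% are ventilated or dead, (1 − 0.25)² = 56% of pairs reach this step. With an assumed flag rate p, the share of all pairs decided here is 0.5625 × 2p(1 − p): 18% at p = 0.2 and 28% at p = 0.5.

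**6. Effect between arms.** If both arms have the same distribution of monitoring, the null win proportion is 0.50. Suppose instead that one arm were read 6 times a day and the other 4 (57.3% versus 47.4% flagged; SD 40, 6 h, 7 days). The more closely monitored arm's null win proportion would be 0.50 − 0.80 × 0.099/2 = 0.46 if 80% of pairs reached the step, or 0.50 − 0.5625 × 0.099/2 = 0.47 if 56% did.

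**The case against.** **The footnote may mean daily averages.** Step 5 and the endpoint definitions use that unit. Two consecutive daily averages would flag 16%, 11% and 11% at 12-, 4- and 1-hourly readings (SD 40, 6 h), so the upward dependence disappears. This stands in part: the frequency problem exists only under the single-reading interpretation and is not independent of the definitional conflict. But the 8-hour baseline makes that interpretation the natural one, and the conflict needs resolving either way.

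**The size is not known.** This stands. It turns on a reading-to-reading SD that the documents do not give. At SD 15 the footnote rule flags only 1%, 2% and 8% at 12-, 4- and 1-hourly readings.

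**A reader might infer that closely monitored patients lose pairs by construction.** The documents do not support that. The rise is not always monotone, and a sustained drop is flagged at any frequency. A flagged patient loses at this step only when both patients survive, tie on ventilator days and the other is unflagged. Closer charting may also follow real worsening, so the extra flags need not be pure noise.

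**A reader might infer bias towards one arm.** Allocation is randomised and stratified and the capsules look identical, so expected monitoring is the same in both arms under the null. Protocol 8.2 says only that the trial is single-blinded, without saying who is blinded. An influence of known treatment on monitoring is therefore possible, but nothing shows it.

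**A reader might infer that many baselines are missing.** If dosing falls at random between readings, the 8-hour window is empty for 1 − 8/12 = 33% of patients read 12-hourly, but for none read 8-hourly or more often. No passage says charting was at the minimum, and SAP 8.4 commits the team to reviewing data to limit missing baselines. A fallback rule is prudent, but the 33% is not a forecast.

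**Conclusion.** The point holds as a contradiction with a measurable consequence. Footnote [3] disagrees with step 5, SAP 5.2.1 and protocol 3.1 on the unit, and with SAP 5.2.1 on the baseline and window. Under its natural reading, the footnote makes the flag depend on charting frequency: about 5% versus 24% (SD 20) to 30% versus 75% (SD 40) for 12-hourly versus hourly readings in patients who do not deteriorate. Those figures rest on an assumed SD and correlation time.

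The expected harm is misclassification and some loss of power in a co-primary endpoint. The loss was not quantified. The synopsis reports enrolment halted at 100 against the 127 required, so there is little room for it. Type I error is not inflated, and no arm is favoured unless treatment, or knowledge of it, changes monitoring.

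The daily average is not free of the problem. A dependence of 4 to 6 points in the opposite direction remains, and it still flags 27% to 33% of stable patients at SD 40. It is better because it removes most of the dependence on charting and is already the stated endpoint.

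**What to change.** In SAP 9.2.1, footnote [3]:

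1. Replace the consecutive-reading rule with the daily-average definition of step 5 and SAP 5.2.1, computed as a time-weighted daily average of SpO2/FiO2.
2. Make the baseline and the time window agree with SAP 5.2.1. SAP 5.2 defines Day 1 as a date, so state whether readings after the first dose count towards the Day 1 value.
3. If the 8-hour baseline is kept, say so in SAP 5.2.1 too, and use the latest earlier pre-dose SpO2/FiO2 pair when that window is empty.

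SAP 10.2 says the final composite analysis differs from the interim only in stratification. If the interim used the footnote rule, that sentence needs a second exception.

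The cost is SAP wording and reprogramming one derived variable. SAP 8.1 starts the final analysis only after SAP approval, so the change belongs in this document. The downsides are that short dips no longer count, a small dependence on charting frequency remains, and a fallback baseline would be older than 8 hours.
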